### **8.2.3. Potential Pitfalls and Alternative Strategies.**

- We will employ a more sensitive technique, called region-of-interest analyses, to detect potential variation in these conditions. Region-of-interest (ROI) analysis involves looking for changes within selected brain areas, instead of looking for changes across the whole brain. As a relatively smaller number of regions will be examined, the overall number of comparisons will be reduced, resulting in an increase in statistical power. Thus, subtle differences between the conditions can be identified. For our purposes, these ROIs would include the ventral striatum, the amygdala and thalamus.
- Humans are not a homogenous group, thus inter-individual variability may pose some difficulty in discerning effects. Variables such as age can have an impact on task parameters. To address this concern, we will (1) perform regression analyses to determine if there is a relationship between these variables and the contrasts of interest and (2)

perform an analysis of covariance (ANCOVA) to control for these variables. The inclusion of covariates in our analyses will increase overall statistical power as variability will be taken into account. In addition, as some groups have reported certain affiliative characteristics to be related to oxytocin measures, we will also be obtaining measures of attachment and sociability that can be used to help explain some of the variation.

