### 8.2.2. Data Analysis & Anticipated Results.

**Analysis of Primary Objective 1 and 2.** Examine the effects of oxytocin on the modified monetary and social incentive delay tasks.

*Analyses.* We will conduct whole-brain voxel-wise analyses with drug (Syntocinon® or Placebo) as a within-subject factor. We will examine the main effects of drug on reward related BOLD activity across the brain during both anticipation and outcome phases.

*Anticipated Results.* As oxytocin administration has been previously demonstrated to reduce amygdala activity in response to social challenges it is hypothesized that we will see a blunting of amygdala reactivity during the anticipation and attainment of social rewards (particularly for negative social incentives). Oxytocin has also been demonstrated to increase dopaminergic activity within the mesolimbic dopamine system (20) so we may see an enhancement of ventral striatal activity during the anticipation of social rewards; however, as Knutson and collaborators have reported that inducing dopamine release within the ventral striatum by amphetamine can actually reduce the difference in BOLD signal activity seen between the anticipation of reward and the anticipation of null (51), reductions in the BOLD response to anticipation of social reward within the ventral striatum is also possible.

While oxytocin has been predominately noted to affect social processes, there is some data to suggest that oxytocin's effects extend beyond modulating affiliative behaviors. Given this, we hypothesize oxytocin administration will show similar, though perhaps diminished, effects on amygdala and ventral striatal activity in response to the anticipation of monetary rewards as we see in anticipation of social rewards.

**Analysis of Primary Objective 3.** Compare responses to the modified monetary incentive delay task in participants with AUD versus controls.

*Analyses.* We will conduct whole-brain voxel-wise analyses with group (AUD or Control) as a within-subject factor. We will examine the main effects of group on reward related BOLD

activity across the brain during both anticipation and outcome phases.

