*Anticipated Results.* It has been observed that individuals with AUD or with a family history of alcoholism show blunted NAc activity during the anticipation of non-drug rewards which may reflect a bias towards alcohol related stimuli. Both the insula and ACING are also implicated in the neurobiology of AUD. Indeed, lower insular activity has been demonstrated to be predictive of relapse and ACING responsivity to the anticipation of monetary reward is inversely related to characteristics associated with AUD including impulsivity. Hence, we expect to observe lower BOLD responses to the anticipation of rewards within the NAc, insula and ACING, in the AUD group compared to controls.

**Analysis of Primary Objective 4.** Compare the effects of oxytocin on the modified monetary incentive delay task in participants with AUD versus controls.

*Analyses.* We will conduct whole-brain voxel-wise analyses with drug (Syntocinon® or Placebo) and group (AUD or Control) as within-subject factors. We will examine the main effects of drug on reward related BOLD activity across the brain during both anticipation and outcome phases and compare this activity between groups.

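### The region-of-interest list in section 8.2.3 leaves out the insula and ACING, which are predicted for Primary Objective 3, and names the thalamus, for which no hypothesis is stated

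*Protocol*

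**What the plan says.** Section 8.2.2 of the protocol states where effects are expected, objective by objective.

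- **Objectives 1 and 2 (drug effect).** For social reward, "we will see a blunting of amygdala reactivity during the anticipation and attainment of social rewards" and "we may see an enhancement of ventral striatal activity during the anticipation of social rewards", with a reduction in the ventral striatum also allowed for. For monetary reward, similar but perhaps weaker "effects on amygdala and ventral striatal activity in response to the anticipation of monetary rewards".
- **Objective 3 (AUD versus control).** "we expect to observe lower BOLD responses to the anticipation of rewards within the NAc, insula and ACING, in the AUD group compared to controls". Reasons are given for each region. For the two that matter here: "Both the insula and ACING are also implicated in the neurobiology of AUD", with insular activity linked to relapse and ACING response linked to impulsivity.
- **Objective 4 (drug effect compared between groups).** No region is named.

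The analysis described for each objective in that section is voxel-wise over the whole brain. Section 8.2.3 then adds: "We will employ a more sensitive technique, called region-of-interest analyses, to detect potential variation in these conditions". The reason given is that fewer regions mean fewer comparisons and more power. The list follows: "these ROIs would include the ventral striatum, the amygdala and thalamus". No other ROI is named in the protocol, apart from the nucleus accumbens in the power statement of section 8.1.

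**The concern.** The ROI analysis is worth having only if it is aimed at the regions where an effect is predicted. For Objective 3 it largely is not. Two of the three regions with a written, directional prediction are missing from the list, and one of the three listed regions has no prediction.

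Followed as written, the insula and ACING hypotheses of a primary objective rest on the approach that the protocol itself treats as less sensitive. A null result there would be hard to read: it could mean no group difference, or only that the whole-brain test could not detect one. A thalamus result would come from the sensitive analysis with nothing stated in advance about direction or reason.

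**Working it through.** **1. Predicted regions against listed regions**

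| Region | Predicted in 8.2.2 for | On the ROI list in 8.2.3 |
|---|---|---|
| Ventral striatum / NAc | Objectives 1, 2 and 3 | Yes |
| Amygdala | Objectives 1 and 2 | Yes |
| Insula | Objective 3 | No |
| ACING | Objective 3 | No |
| Thalamus | None | Yes |

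The NAc counts as covered because it lies within the ventral striatum. The protocol does not expand ACING. Anterior cingulate is the natural reading, but the mismatch does not depend on it, since the term is not on the list. For Objectives 1 and 2 both predicted regions are listed. For Objective 3, one of three is.

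**2. The plan's own power figure**

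Inputs: section 8.1 gives 44 subjects, effect size 0.77 SD, one-sided 0.005, at least 90% power, nucleus accumbens. Section 3 gives 44 controls and 44 AUD participants.

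Power = 1 − F(t₁₋α,df ; df, δ), where F is the noncentral t distribution function.

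- One-sample or paired test, n = 44: df = 43, δ = 0.77 × √44 = 5.11, power 99.0%. This is consistent with at least 90%, though well above it.
- Two-sample test, 44 versus 44 (the Objective 3 comparison): df = 86, δ = 0.77 × √(44/2) = 3.61, power 83.3%.

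So the stated figure fits a within-group or paired contrast, and it covers only the nucleus accumbens. It says nothing about the insula or ACING.

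**3. What extra ROIs could cost**

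The protocol does not say whether 0.005 applies to each ROI or is shared. As an illustration, take the two-sample formula, assume d = 0.77 in each region, and divide 0.005 equally:

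| ROIs sharing 0.005 | One-sided threshold per region | Power per region |
|---|---|---|
| Not shared | 0.005 | 83.3% |
| Three | 0.005/3 = 0.00167 | 72.1% |
| Five | 0.005/5 = 0.001 | 66.3% |

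Three is the number for Objective 3 if ROIs are assigned by objective. Five is the number if insula and ACING are simply appended to the present list and all regions share one threshold.

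**4. What cannot be computed**

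The sensitivity lost by leaving the insula and ACING to the whole-brain test depends on the whole-brain threshold and on the true effect in those regions. The protocol gives neither.

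**The case against.** Several points on the other side have weight.

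- **The list is worded as open**, and it stands under pitfalls and alternative strategies. Final ROI sets and masks are often fixed in an SAP, which may exist. This softens the point. It does not remove it: the protocol chose to name regions, and those named do not match its own hypotheses.
- **The list may be meant only for the drug contrast.** Section 8.2.3 speaks of conditions. Section 8.2.1 uses that word for drug and placebo, while AUD and control are called groups. On that reading two of the three listed regions are exactly those predicted for Objectives 1 and 2. The wording is ambiguous. If this reading is right, however, Objective 3 has no ROI list at all, and the thalamus still has no hypothesis.
- **The regions are still tested.** A reader might infer that the insula and ACING predictions go unexamined. They do not: the whole-brain analysis covers both.
- **The loss might look large and measurable.** One could set 83% at the ROI threshold against the much lower power at strict voxel thresholds. That comparison is not supported. It puts an uncorrected ROI threshold beside assumed multiplicity-driven ones, borrows a d stated only for the nucleus accumbens, and takes the effect to be equal in an ROI average and a single voxel. With five ROIs sharing 0.005, power per ROI is 66.3%, the same as at a voxel threshold of 0.001, because the two thresholds are then identical.
- **Later addition might look data-driven.** For the insula and ACING it would not be, since both are already predicted in writing with a direction.
- **The thalamus might seem to use up error rate.** No shared threshold is stated, so no cost to the other regions is shown.

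**Conclusion.** The mismatch is real and can be read directly from sections 8.2.2 and 8.2.3. Two of the three regions predicted for Objective 3 are not on the only ROI list in the protocol, and one of the three listed regions has no hypothesis. The consequence is reduced sensitivity for the insula and ACING predictions, by an amount that the protocol does not allow anyone to state.

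The conclusion rests on taking the list as written and on counting the NAc as part of the ventral striatum. It depends on no computed figure; the power numbers only illustrate the price of the remedy. It does not show that a whole-brain analysis, the sample size or an error rate is wrong. It is a worthwhile and inexpensive correction to a supplementary analysis of a primary objective.

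**What to change.** Amend section 8.2.3 to assign ROIs by objective:

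- Objectives 1 and 2: ventral striatum and amygdala.
- Objective 3: ventral striatum/NAc, insula and ACING, with ACING spelled out.
- Thalamus: labelled exploratory, unless a hypothesis for it is added to section 8.2.2.

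Objective 4 has no regional prediction in section 8.2.2, so this change assigns it no regions.

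State also whether the 0.005 threshold applies to each ROI or is shared within an objective. Section 2.2.1 places all group-level analyses after the last participant's final scan follow-up, so an amendment made before then keeps the ROI set prespecified.

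The cost is a few lines of text and two extra masks, with no change to sample size or procedures. If a threshold is shared, each region faces a stricter one: in the illustration above, power falls from 83% to 72% with three ROIs. Assigning ROIs by objective keeps the Objective 3 set at three, the same number as the present list, and avoids the further fall to 66% that a pooled set of five would bring.

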### **8.3. Safety Analysis**

Adverse event data will be recorded and reported to the data safety monitor.

## **9. MONITORING**

### **9.1. Monitoring Plan and Information**

To assure adequate protection of the rights of human subjects, per 21 CFR §312.50, 312.53, the study will be monitored to ensure proper informed consent procedures were followed and to ensure the quality and integrity of the data.

### **9.2. Safety Monitoring**

This study will utilize study monitors within the Clinical Trials Office at the University of Utah School of Medicine. This unit specializes in providing clinical investigators with research support services and has experience overseeing projects from Phase I-IV and supporting IND/IDE projects. The monitoring team helps researchers develop and implement monitoring and auditing plans, aids researchers in IRB submission, maintains regulatory files and coordinates with the FDA and NIH when necessary.

Taking into account the objective, purpose, design, complexity, size and endpoints of this study, the following monitoring will occur:

- 100% monitoring of the first two subjects
- 100% monitoring of informed consent documents
- 100% monitoring of protocol deviations
- 100% monitoring of adverse events
- Monitoring of essential documents

Monitoring will occur on an annual basis. Following each visit, the monitor will generate a monitoring report to describe the progress of the study, any visit findings, and identify needed follow up. These reports will be available to all study team members, including other monitors, study management, and data management. All open action items will be reviewed for completion at consecutive monitoring visits. The monitoring report will include, but will not be limited to, the following:

- The date of the monitoring visit, and the individual(s) conducting it
- A list of subject records reviewed (e.g. subject charts, hospital records, lab slips, etc.) as well as case report forms reviewed
- A description of any noncompliance, potential noncompliance, data discrepancies, or other deficiencies identified
- A description of any actions taken, to be taken, or recommended actions, as well as the person responsible for completing action items.

## **10. DATA HANDLING AND RECORD KEEPING**

To ensure confidentiality of patient information, study data will be collected and managed using an encrypted, 21 CFR Part 11 and HIPAA-Compliant electronic database system, REDCap (Research Electronic Data Capture). REDCap is a secure web application designed to support data capture for research studies, providing user-friendly web-based case report forms, real-time data entry validation (e.g. for data types and range checks), audit trails, electronic signatures, and Standard Operating Procedures (SOPs) that protect data confidentiality and integrity. REDCap has been disseminated for use locally and currently supports over 240+ academic/non-profit consortium partners on six continents and over 26,000 research end-users ([www.project-redcap.org](http://www.project-redcap.org)). The REDCap software was developed by Vanderbilt University and has been obtained and installed for usage at the University of Utah. All access to the data requires individual authentication (a unique username and password) and all data into and out of the server is encrypted, which prevents eavesdropping and tampering with any transmitted data, and is the standard for encrypting communications across all industries, including financial services and healthcare.

### **10.1. Record Retention**

Per 21 CFR §312.62, study records will be retained for at least 2 years after the investigation is discontinued.

### **10.2. Annual Progress Report**

An annual progress report will be submitted to the FDA within 60 days of the anniversary of the date that the IND went into effect per 21 CFR §312.33.

## **11. ETHICS**

### **11.1. IRB/FDA**

Prior to study commencement, an Investigator Initiated Investigational New Drug (IND) request will be submitted to the Food and Drug Administration (FDA), for review and approval. The study will also be reviewed and approved by the Institutional Review Board (IRB, University of Utah, Salt Lake City, UT).

This study will be carried out in compliance with the protocol and the principles of Good Clinical Practice.

Before implementing this study, the protocol, the proposed informed consent form and other information to be provided to subjects, must be reviewed by a properly constituted Institutional Review Board (IRB). Any amendments or administrative changes in the research protocol during the period, for which the IRB approval has already been given, will not be initiated without submission of an amendment for IRB review and approval. Any amendments to the protocol that significantly affect the safety of subjects, scope of the investigation, or the scientific quality of the study will be submitted for FDA review. These requirements for approval will in no way prevent any immediate action from being taken by the investigator in the interests of preserving the safety of all patients included in the trial.

### **11.2. Protocol Deviations**

A protocol deviation (or violation) is defined as any departure from the defined procedures

and treatment plans as outlined in the protocol version submitted and previously approved by the IRB. Protocol deviations have the potential to place participants at risk and can also undermine the scientific integrity of the study thus jeopardizing the justification for the research. Protocol deviations are unplanned and unintentional events.

Because some protocol deviations pose no conceivable threat to participant safety or scientific integrity, reporting is left to the discretion of the PI within the context of the guidelines below. The IRB/FDA will be promptly notified of protocol deviations which are:

- Exceptions to eligibility criteria.
- Intended to eliminate apparent immediate hazard to a research participant
- Harmful (caused harm to participants or others, or place them at increased risk of harm—including physical, psychological, economic, or social harm)
- Possible serious or continued noncompliance

### **11.3. Subject Information and Consent**

The study team member will explain to each subject (or legally authorized representative) the nature of the study, its purpose, the procedures involved, the expected duration, the potential risks and benefits involved and any discomfort it may entail. Each subject will be informed that participation in the study is voluntary and that he/she may withdraw from the study at any time and that withdrawal of consent will not affect his/her subsequent medical treatment or relationship with the treating physician.

This informed consent will be given by means of a standard written statement, written in non-technical language. The subject should read and consider the statement before signing and dating it, and should be given a copy of the signed document. If the subject cannot read or sign the documents, oral presentation may be made or signature given by the subject's legally appointed representative, if witnessed by a person not involved in the study, mentioning that the patient could not read or sign the documents. No patient can enter the study before his/her informed consent has been obtained.

The informed consent form is considered to be part of the protocol, and will be submitted for IRB approval.

## **12. STUDY DISCONTINUATION CRITERIA**

The study team will review all Serious Adverse Events (SAEs) and make recommendations regarding the continuation or discontinuation of the study. The study will be stopped or the protocols modified when there is sufficient evidence of unacceptable side effects of the study drug or placebo. Participants are free to leave the study at any time without any penalty. If the participant chooses to tell the study team why they are leaving the study, the reasons will be kept as part of the study record.

Patients can be discontinued from the study for a variety of reasons including:

- The researcher feels it is not in the best interest of the participant to stay in the study
- The participant does not follow instructions
- The participant becomes ineligible to participate

- The participant's condition changes and they require treatment which is not allowed to be taken during the study
- The study is suspended or cancelled

